**Table 4.5.2-1: Dose Modifications**

Dose Modification Criteria for Drug-Related Adverse Events	BMS-986148 (Parts 1, 2, and 3) (Modification at Next Dose)
Any other drug-related $\geq$ Grade 3 nonhematologic AE (except in subjects not receiving maximum medical management or electrolyte abnormalities that may be managed with supplements ) that does not meet permanent discontinuation criteria (Section 3.5).	Decrease 1 level.

a Reduction in visual acuity is defined as 20/40 or worse and at least 2-line reduction from baseline visual acuity and accompanied by symptoms limiting age appropriate instrumental ADL or diagnostic observations.  
ADL: activities of daily living; AE: adverse event; ALT: alanine transaminase; AST: aspartate transaminase; ECG: electrocardiogram; PI: principal investigator; QTcF: QT interval corrected by Fridericia’s formula; ULN: upper limit of normal.

### **4.5.3 Dose Delay Criteria (Applicable for Part 3)**

Subjects who experience a DLT must have both study drugs held. Every attempt must be made to assign relationship to BMS-986148, to nivolumab, or to both. If the toxicity is attributed to BMS-986148 (eg, early onset liver function tests [LFT] abnormalities or AEs similar to profile determined from monotherapy cohorts) will lead to dose modification of BMS-986148 according to [Table 4.5.2-1](#) and nivolumab can be resumed. Similarly if the toxicity is attributed to nivolumab (eg, pneumonitis), dosing of nivolumab can be delayed or discontinued per the guidelines below and BMS-986148 can be resumed. Such modifications should be discussed and agreed upon by the BMS Medical Monitor and investigators. In addition, all Grade 2 hepatic, pulmonary, renal, gastrointestinal, and neurological AEs seen with nivolumab should be evaluated and managed per the toxicity management algorithms ([Appendix 3](#)). Subjects not meeting guidelines for permanent discontinuation will be permitted to resume therapy based on the criteria specified in [Table 4.5.2-1](#). Subjects eligible to resume study therapy will resume study therapy at the treatment visit following their last received study drug dose.

The end-of-cycle tumor assessments (ie, CT/MRI, positron emission tomography, etc) will continue on an every-6-week schedule relative to the subject's first dose regardless of any treatment delay incurred.

Study drug administration should be delayed for the following:

- Any Grade  $\geq 2$  nonskin, drug-related AE, with the following exception:
  - Grade 2 drug-related fatigue does not require a treatment delay.
- Grade 2 drug-related creatinine, AST, ALT, or TB abnormalities
- Any Grade 3 skin, drug-related AE
- Any Grade 3 drug-related laboratory abnormality (excluding AST, ALT, or TB), with the following exceptions for lymphopenia and asymptomatic amylase or lipase:
  - Grade 3 lymphopenia does not require dose delay.
  - Any Grade  $\geq 3$  drug-related amylase or lipase abnormality that is not associated with symptoms or clinical manifestations of pancreatitis does not require dose delay.
- Any AE, laboratory abnormality, or intercurrent illness that, in the judgment of the investigator, warrants delaying the dose of study medication.

Subjects who require delay of study drugs should be re-evaluated QW or more frequently if clinically indicated and resume nivolumab dosing when retreatment criteria are met.

For data collection and analysis purposes, all subjects will continue to be classified by the original treatment arm.

### **4.5.4 Criteria to Resume Treatment for Part 3**

Subjects may resume treatment with study drugs when the drug-related AE(s) resolves to Grade  $\leq 1$  or baseline value, with the following exceptions:

- Subjects may resume treatment in the presence of Grade 2 fatigue.

- Subjects who have not experienced a Grade 3 drug-related skin AE may resume treatment in the presence of Grade 2 skin toxicity.
- For subjects with Grade 2 creatinine, AST, ALT, or TB elevations, dosing may resume when laboratory values return to baseline, and management with corticosteroids, if needed, is complete.
- Subjects with combined Grade 2 AST/ALT AND TB values meeting discontinuation parameters ([Section 3.5](#)) should have treatment permanently discontinued.
- Drug-related pulmonary toxicity, diarrhea, or colitis must have resolved to baseline before treatment is resumed. Subjects with persistent Grade 1 pneumonitis after completion of a steroid taper over at least 1 month may be eligible for retreatment if discussed with and approved by BMS Medical Monitor.
- Subjects with drug-related endocrinopathies adequately controlled with only physiologic hormone replacement may resume treatment after consultation with the BMS Medical Monitor.

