### **1.5.2 Risk/Benefit for BMS-986148 and Nivolumab Combination Therapy**

Nivolumab has demonstrated clinical activity in subjects with advanced NSCLC, renal cell carcinoma, melanoma, and lymphomas, as well as other tumors, including ovarian, gastric, and mesothelioma. The clinical activity of nivolumab monotherapy observed to date in these malignancies suggests the potential for improved clinical outcomes relative to other approved therapies.

Nivolumab has demonstrated a manageable safety profile. The overall safety experience, when used either as a monotherapy or in combination with another therapeutic, is based on experience in approximately 8,600 subjects treated to date. There is no pattern in the incidence, severity, or causality of AEs with respect to nivolumab dose level. The most common AEs (as of 01 July

2016) include fatigue, rash, pruritus, diarrhea, and nausea. Side effects of nivolumab therapy may include those associated with immune-mediated activation, such as pneumonitis, thyroiditis, and hepatitis. Most of these events resolved with immune-modulating medication. To mitigate risk from serious immune-mediated AEs, subject management algorithms for nivolumab-related AEs from prior collective nivolumab experience have been included ([Appendix 3](#)).

There is potential for overlapping toxicity between clinical findings of BMS-986148 and nivolumab-related hepatotoxicity, infusion-related reactions, and peripheral neuropathy.

Elevation of the liver transaminases were the DLTs noted in 4 of the 10 subjects treated with BMS-986148 at 1.6 mg/kg Q3W. This dose is above the MTD, and no additional subjects will be treated at this dose. At the selected starting dose of BMS-986148 of 0.8 mg/kg IV Q3W, no DLTs were observed in the 4 evaluable subjects. However, the incidence of nivolumab-related hepatitis is quite low (approximately 1%). Subjects in this study receiving BMS-986148 monotherapy or BMS-986148 and nivolumab combination therapy will be monitored closely for any LFT abnormalities via laboratory assessments and frequent assessment for the development of symptoms. Study drug will be discontinued for any significant LFT abnormalities.

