### **3.5 Discontinuation of Subjects following any Treatment with Study Drug**

Subjects **MUST** discontinue investigational product (and noninvestigational product at the discretion of the investigator) for any of the following reasons:

- Subject's request to stop study treatment and/or participation in the study
- Any clinical AE, laboratory abnormality, or intercurrent illness which, in the opinion of the investigator, indicates that continued participation in the study is not in the best interest of the subject
- Termination of the study by BMS
- Loss of ability to freely provide consent through imprisonment or involuntarily incarceration for treatment of either a psychiatric or physical (eg, infectious disease) illness
- Inability to comply with protocol
- Discretion of the investigator

- Confirmed CR as defined by RECIST version 1.1 or Modified RECIST for malignant pleural mesothelioma (see [Appendix 4](#)) unless subject meets criteria to continue treatment with nivolumab
- Documented disease progression as defined by RECIST version 1.1 or Modified RECIST criteria for malignant pleural mesothelioma (see [Appendix 4](#)) unless subject meets criteria for treatment beyond progression ([Section 4.5](#)) (for subjects in Part 3)
- AE(s) requiring discontinuation as outlined in the Dose Modification section (See [Section 4.5.2](#))

In the case of pregnancy, the investigator must immediately notify the BMS Medical Monitor/designee of this event. In most cases, the study drug will be permanently discontinued in an appropriate manner. If the investigator determines a possible favorable benefit/risk ratio that warrants continuation of study drug, a discussion between the investigator and the BMS Medical Monitor/designee must occur.

All subjects who discontinue investigational product should comply with protocol specified follow-up procedures as outlined in [Section 5](#). The only exception to this requirement is when a subject withdraws consent for all study procedures including post-treatment study follow-up or loses the ability to consent freely (ie, is imprisoned or involuntarily incarcerated for the treatment of either a psychiatric or physical illness).

If study drug is discontinued prior to the subject's completion of the study, the reason for the discontinuation must be documented in the subject's medical records and entered on the appropriate CRF page.

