**Table 4.5.2-1: Dose Modifications**

Dose Modification Criteria for Drug-Related Adverse Events	BMS-986148 (Parts 1, 2, and 3) (Modification at Next Dose)
Grade 4 neutropenia lasting > 5 days	Decrease 1 level.
Grade 3 febrile neutropenia lasting > 48 hours	Decrease 1 level.
Grade 4 febrile neutropenia	Discontinue.
Grade 4 thrombocytopenia or ≥ Grade 3 thrombocytopenia with clinically significant bleeding	Decrease 1 level.
QTcF > 500 msec confirmed by at least 1 repeat ECG and at least 60 msec above baseline	Interrupt if needed to optimize electrolyte management; if persists after electrolyte optimization (including dose modification of BMS-986148, if necessary), discontinue.
Grade 1 Troponin I or T confirmed when repeated in 72 hours	Discontinue.
Grade 3 Troponin I or T	Discontinue.
AST or ALT > 5 times the institutional ULN that last ≥ 5 days or is symptomatic	Decrease 1 level.
≥ Grade 3 infusion-related reaction	See Section 3.4.1 .
≥ Grade 3 peripheral neuropathy	Discontinue.
≥ Grade 2 uveitis or eye pain or reduction in visual acuity a that improve to Grade 1 within 2 weeks of initiation of topical therapy	Interrupt dosing until improvement to Grade 1 or baseline and decrease 1 level.
≥ Grade 2 uveitis or eye pain or reduction in visual acuity a that does not respond to topical therapy and that does not improve to Grade 1 within 2 weeks of initiation of topical therapy	Discontinue.
≥ Grade 3 eye symptoms	After improvement to Grade 1 or baseline, additional therapy with BMS-986148 (decrease 1 level) may be considered after discussion and agreement by the BMS Medical Monitor and investigators that it is in the best interest of the subject (for example, if the subject has demonstrated a response to therapy).
≥ Grade 3 eye symptoms	Discontinue.

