### 6.6 Potential Drug-Induced Liver Injury

Wherever possible, timely confirmation of initial liver-related laboratory abnormalities should occur prior to the reporting of a p-DILI event. All occurrences of p-DILIs, meeting the defined criteria, must be reported as SAEs (see Section 6.1.1 for reporting details). The criteria for identifying p-DILI events depend on whether the subject's baseline liver biochemistry is normal or abnormal (see Figure 6.6-1).

**Figure 6.6-1: Algorithm for p-DILI Identification and Mandatory SAE Reporting in Subjects with (i) Normal Baseline Liver Biochemistry and (ii) Abnormal Baseline Liver Biochemistry**

ALT: alanine transaminase; AST: aspartate transaminase; SAE: serious adverse event; p-DILI: potential drug-induced liver injury; TB: total bilirubin; ULN: upper limit of normal.

The key responsibilities for investigators during p-DILI assessment include: (i) Early detection, medical evaluation (including the exclusion of other potential causes), and rapid laboratory confirmation of liver-related abnormalities, and (ii) BMS notification of p-DILI cases via SAE forms. Following the gathering and assessment of relevant clinical information BMS is responsible for: (iii) Timely evaluation and triaging of p-DILI cases, (iv) Expedited reporting of p-DILI cases, and (v) Expanded review of p-DILI cases including a detailed assessment of all available clinical information, investigations, and biochemical data.

Investigators are expected to monitor ongoing routine and ad hoc hepatic laboratory test results to rapidly determine whether a subject meets p-DILI criteria. They are expected to promptly notify BMS of all p-DILI cases. p-DILI cases may be identified by abnormal liver biochemistry values, whether or not they are accompanied by liver-related signs and/or symptoms. In both cases, expedited confirmation with repeat laboratory testing should occur within 3 business days using a Hepatic Laboratory Panel (ALT, AST, TB, and alkaline phosphatase). Any subject with an abnormal Hepatic Laboratory Panel that meets p-DILI criteria (see [Figure 6.6-1](#)) is a candidate for study drug discontinuation. Any confirmed p-DILI events must be reported (along with a description of the clinical findings) to BMS as an SAE within 24 hours of confirmation.

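### A Part 3 liver stopping rule in Protocol Section 4.5.4 cites parameters that are not in Section 3.5, and Section 1.5.2 disagrees with Table 4.5.2-1 on the action for raised transaminases

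*Protocol*

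**What the plan says.** Five places in the Protocol bear on this point.

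- **Section 4.5.4** (resuming treatment, Part 3). Subjects with Grade 2 AST, ALT or bilirubin elevation may resume once values are back at baseline and any steroid course is finished. The next bullet makes an exception: "Subjects with combined Grade 2 AST/ALT AND TB values meeting discontinuation parameters", with a reference to Section 3.5, are to stop permanently.
- **Section 3.5** (discontinuation). The list contains no liver laboratory value. The two entries that could apply are the investigator's opinion that an event or laboratory abnormality makes continuing unwise, and "AE(s) requiring discontinuation as outlined in the Dose Modification section", which sends the reader to Section 4.5.2.
- **Table 4.5.2-1**. The only row naming liver tests is "AST or ALT > 5 times the institutional ULN that last ≥ 5 days or is symptomatic", with the action of reducing BMS-986148 by one level. The closing row covers any other drug-related nonhematologic event of Grade 3 or above "that does not meet permanent discontinuation criteria (Section 3.5"), and also reduces by one level.
- **Section 1.5.2** (risk/benefit). After stating that subjects on monotherapy and on the combination will be watched for liver test abnormalities, it says: "Study drug will be discontinued for any significant LFT abnormalities".
- **Section 4.5.3** (delay, Part 3). Both drugs are held for a DLT. The section then says what follows if the event is attributed to BMS-986148, and what follows if it is attributed to nivolumab.

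**The concern.** Section 4.5.4 states a mandatory permanent stop, but its trigger cannot be found by following the reference. Two sites with the same Part 3 subject could act differently, one resuming at baseline and the other stopping, and each could defend its reading. Section 1.5.2 adds a second ambiguity, because it describes to ethics committees and investigators a firmer action than the operational table contains.

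The organ matters. Section 1.5.2 reports transaminase elevation as the DLT in 4 of 10 subjects at 1.6 mg/kg and lists hepatotoxicity among the possible overlapping toxicities with nivolumab. Section 7 provides for no data monitoring committee, so the written rules carry more of the load. Adverse events leading to discontinuation are also a component of the primary endpoint (Section 8.3.1), and SAP Section 7.6.4 counts them from the recorded action taken. Uneven site action could therefore enter that count, although the documents give no basis for estimating by how much.

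**Working it through.** No sample size, power or alpha figure is involved. The check is a trace of the cross-references, followed by two test subjects.

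**The reference chain**

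1. Section 4.5.4 cites Section 3.5 for the combined AST/ALT and bilirubin parameters.
2. Section 3.5 holds none and shows no redaction mark. It points to Section 4.5.2.
3. Table 4.5.2-1 has one row naming AST or ALT, with a reduction as the action. It has no combined row. Its closing row starts at Grade 3, so a combined Grade 2 picture does not reach it.
4. That closing row refers back to Section 3.5 for permanent discontinuation criteria.

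The chain is 4.5.4 → 3.5 → 4.5.2 and Table 4.5.2-1 → 3.5. The only exit is the investigator-judgment entry in Section 3.5, which is not a parameter of the kind Section 4.5.4 describes.

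**Subject A: Part 3, drug-related combined Grade 2 AST/ALT and bilirubin**

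- Section 4.5.3 delays dosing ("Grade 2 drug-related creatinine, AST, ALT, or TB abnormalities").
- Section 4.5.4 then allows resumption at baseline, or requires a permanent stop if the uncited-in-fact parameters are met.
- Table 4.5.2-1 has no row for this subject.
- Result: the choice between resuming and stopping cannot be settled from the text as referenced.

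**Subject B: AST/ALT 6 times ULN for 6 days, no symptoms, normal bilirubin**

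- The Table 4.5.2-1 row is met (6 > 5 times ULN; 6 ≥ 5 days): reduce BMS-986148 one level.
- Section 1.5.2: discontinue study drug if the abnormality is significant. That word is not defined, and an event that meets a dose-modification row is hard to call insignificant.
- In Part 3, if attributed to BMS-986148 alone, Section 4.5.3 sends the event to Table 4.5.2-1 and lets nivolumab resume. Section 4.5.5 defers to the same table for BMS-986148. These agree with one another, and the conflict is with Section 1.5.2.
- In Part 3, if attributed to both drugs, Section 4.5.3 holds both and then gives no next step. Section 4.5.5 says only that nivolumab is discontinued and/or BMS-986148 modified.

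**Reach**

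Part 3 planned subjects: 12 in Part 3A plus 125 to 150 in Part 3B, so 12 + 125 = 137 and 12 + 150 = 162. The unresolved reference affects those among them who develop combined Grade 2 elevations. The documents give no expected number.

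**The case against.** The strongest defence is that most liver events are covered. Several stronger readings that a reader might draw are not supported.

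- **That Grade 3 liver events fall through.** Section 4.5.3 does carve them out of one bullet ("Any Grade 3 drug-related laboratory abnormality (excluding AST, ALT, or TB"), but its first bullet still delays for any nonskin drug-related event of Grade 2 or above. Section 4.5.5 takes up anything meeting the DLT criteria of Section 4.5.1. There, Grade 3 transaminase elevation counts unless it is short, without symptoms and without bilirubin above 2 times ULN.
- **That many passages give contradictory actions for one subject.** Most differences depend on drug, grade or attribution. In Section 6.6, a subject meeting potential drug-induced liver injury criteria "is a candidate for study drug discontinuation", which is permissive and compatible with reducing or stopping. Appendix 3 addresses immuno-oncology therapy. The direct conflict is one pair: Section 1.5.2 against Table 4.5.2-1.
- **That a large transaminase rise with raised bilirubin exposes the gap.** The Section 4.5.4 bullet concerns Grade 2 values, so such a case does not test it.
- **That all 316 to 366 planned subjects (179 + 137 to 204 + 162) are affected.** The unresolved reference is in a Part 3 section only.

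It can also be said that Section 1.5.2 is narrative, that Section 4.5.2 calls its criteria general guidelines, and that the investigator and Medical Monitor can always act more cautiously. All of that stands, and it means a subject can be stopped when judgment calls for it. None of it supplies the parameters that Section 4.5.4 says exist.

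Figure 6.6-1 and the hepatic algorithm figure are not visible in the text reviewed and may contain combined thresholds. If so, Section 4.5.4 may simply carry a wrong reference. It would still need correcting, because it cites neither.

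**Conclusion.** The point holds as an internal inconsistency that should be fixed, in three parts.

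- **(a)** The permanent-stop bullet in Section 4.5.4 cannot be applied as referenced.
- **(b)** Section 1.5.2 and Table 4.5.2-1 state different actions for raised transaminases. This pair is not confined to Part 3, since both texts cover monotherapy and combination.
- **(c)** As a minor matter, the case of attribution to both drugs has no stated follow-on in Section 4.5.3.

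Part (a) is limited to combined Grade 2 elevations within the 137 to 162 planned Part 3 subjects. The link to the reported DLTs is the same organ, not the same laboratory pattern: those 4 of 10 events were monotherapy transaminase elevations at a dose that Section 1.5.2 says is above the MTD and will not be used again. Any effect on the discontinuation endpoint is possible but not quantified. The conclusion assumes that nothing relevant in Section 3.5 was lost in text extraction; no redaction mark appears there.

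**What to change.** Reconcile Sections 1.5.2, 3.5, 4.5.3 and 4.5.4 and Table 4.5.2-1 in the next amendment:

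- make Section 4.5.4 point to a place that actually states the combined AST/ALT and bilirubin discontinuation parameters;
- bring the Section 1.5.2 statement and Table 4.5.2-1 into agreement, and define or remove the undefined adjective;
- state in Section 4.5.3 what follows when an event is attributed to both drugs.

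The sponsor's clinical team decides every threshold and action; none is suggested here. The cost is amendment wording and its ethics review. No test, visit or analysis needs to be added.

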#### **4.5.5 Study Drug Discontinuation (Part 3)**

In certain circumstances of nivolumab-related AE's requiring discontinuation that do not overlap with known BMS-986148 toxicities, eg, pneumonitis, BMS-986148 can be resumed after discussion with the Sponsor/Medical Monitor if is in the best interest of the subject to receive additional therapy with BMS-986148 (for example, if the subject has demonstrated a response to therapy):

- Any drug-related AE occurring at any time that meets DLT criteria as outlined in [Section 4.5.1](#) will require discontinuation of nivolumab and/or dose modification of BMS-986148 ([Table 4.5.2-1](#)), with the exception of the following:
  - Grade 3 diarrhea, nausea, vomiting, or abdominal pain that returns to Grade 1 or baseline within 3 days with medical intervention
  - Grade 3 pruritus or rash that returns to Grade 1 or baseline within 7 days, or baseline with medical intervention;
  - Isolated Grade 3 or 4 electrolyte imbalances/abnormalities that are not associated with clinical sequelae and are corrected with supplementation/appropriate management within 72 hours of their onset
  - Grade 4 neutropenia < 5 days in duration
  - Grade 4 lymphopenia or leukopenia
  - Grade 3 or 4 increase in amylase or lipase that is not associated with clinical or radiographic evidence of pancreatitis
  - Grade 3 or 4 drug-related endocrinopathy AEs, such as adrenal insufficiency, adrenocorticotrophic hormone deficiency, hyper- or hypothyroidism, or glucose intolerance, which resolve or are adequately controlled with physiologic hormone replacement (corticosteroids, thyroid hormones) or glucose-controlling agents, respectively, may not require discontinuation after discussion with and approval from the BMS Medical Monitor

- ◆ Dosing delays to allow for prolonged steroid tapers to manage drug-related AEs are allowed. Prior to reinitiating treatment in a subject with a dosing delay lasting > 6 weeks from the previous dose, the BMS Medical Monitor must be consulted. Tumor assessments should continue as per protocol even if dosing is delayed. Periodic study visits to assess safety and laboratory studies should also continue Q6W for Parts 1A, 2, and 3 and every 8 weeks [Q8W] for Part 1B or more frequently if clinically indicated during such dosing delays.
- ◆ Dosing delays lasting > 6 weeks from the previous dose that occur for nondrug-related reasons may be allowed if approved by the BMS Medical Monitor. Prior to reinitiating treatment in a subject with a dosing delay lasting > 6 weeks, the BMS Medical Monitor must be consulted. Tumor assessments should continue as per protocol even if dosing is delayed. Periodic study visits to assess safety and laboratory studies should also continue Q6W or more frequently if clinically indicated during such dosing delays.
- Any AE, laboratory abnormality, or intercurrent illness, which, in the judgment of the investigator, presents a substantial clinical risk to the subject with continued nivolumab dosing.

